### **Injection site reactions**

In this clinical study, investigators will evaluate injection site reactions after the administration of BCD-085/placebo. Assessments will be performed on the same visits when injections will be given. Assessment includes visual examination of the injection site (and sites where injections were given in the past if this is not the first visit) and collection of patient's complaints. The Injection Site Reaction Form is presented in Annex 1. The Injection Site Reaction Report Form should be filled out only if an injection site reaction is recorded (starting from grade 1). If there are no injection site reactions, this form is not filled out. Injection site reactions of grade 2 or higher must be registered as adverse reactions. If the investigator considers a grade 1 injection site reaction to be clinically meaningful, it also must be registered as an adverse event. Severity grades for injection site reactions are presented in Annex 1.

**Among other laboratory/vital sign/clinical abnormalities not found at Visit 1 before the first injection of the investigational product, the following is recorded:**

- All abnormalities of CTCAE 4.03 grade 2 and higher.
- Grade 1 abnormalities should be recorded as AEs only if clinically relevant, i.e. if the Investigator considers the abnormality to be substantial with account of the main and concurrent illnesses. Single abnormalities found among multiple laboratory test results or

---

 If retest is performed, its results are considered.

incidental low values should not be reported as AEs, except for events that are clinically relevant.

If revealed during the period between scheduled visits (for example, when the patient comes to the study site for dialysis), a laboratory/vital sign/instrumental abnormality can be recorded by the Investigator in the eCRF if clinically meaningful (regardless of its severity grade). The Investigator specifies the onset date, the fact that the AE occurred between visits, and the reason why the AE was recorded (for example, numerical values of laboratory and/or vital signs).

### **8.3.2. AE/SAE reporting**

The AE Report Form should be filled out during the study visit (or the investigator can do it later the same day), except for data not available/not known at that moment. All sections of the form must be filled out. If no data are available, “Data not available” or “N/A” are put. However, all actions should be taken to receive all necessary data on emerging adverse events.

The following information is recorded in source documents and the AE Report Form of the CRF:

- Sec. No. of AE,
- Visit number,
- A brief description of the AE,
- Serious (yes/no),
- Seriousness criteria (if applicable),
- Severity grade and highest severity grade according to CTCAE 4.03,
- Onset date,
- End date,
- Outcome,
- Actions taken,
- Causality,
- Comments specifying any clinically relevant (in the Investigator’s opinion) information related to AE development or therapy.

If a medication therapy was administered, its components are described in section “Concomitant therapy” of the CRF, with a notice that a medication was used to manage the AE.

Columns *Grade*, *Outcome*, *Measures*, and *Causal Relationship* are filled using digital codes explained in the *Notes* section. If the investigator considers an AE to be an SAE, he/she fills out an SAE Report Form in addition to the AE Report Form (printed copies).

One SAE Report Form is filled out for one SAE. If the AE remains unresolved at the next visit, the checkbox in the *Adverse Events* section of the eCRF should be ticked for this visit and marked as “unresolved”. If any new important information has become available, a follow-up SAE Report Form should be filled out and sent to the Sponsor. If no new information about the SAE is available, the recommended frequency of reporting is once every 14 days.

The following information should be recorded in the SAE Report Form:

1) Clinical study:

- Protocol ID,

2) SAE information:

- SAE name,
- Initial or follow-up,
- Internal SAE code assigned by the Sponsor (this field is filled out by the Sponsor)

3) SAE reporting investigator and study site:

- Full name of the investigator who reported the SAE
- Contact information (tel. and e-mail)
- Site name and code
- Full name of the Principal Investigator

4) Information on the study subject:

- Subject's number
- Sex
- Body weight
- Height
- Date of birth
- Renal/hepatic impairment
- Allergies

5) Information on the test drug:

- Code (or trade name) of investigational product
- Indication
- Date of the first dose

Translated from Russian to English, dated 26-Nov-2019

- Batch of the investigational product (after which the event developed)
- Dose (with which the event occurred)
- Treatment start date and time (followed by the event)
- Treatment stop date and time (followed by the event)
- Route of administration
- Doses and dosing frequency

6) Information about recent (within one month) concomitant therapy or one used at the time of SAE onset:

- INNs and brand names of concomitant medications
- Indication
- Start date
- End date
- Doses, frequency and route of administration
- Any suspected causal relationship between the SAE and concomitant medications

7) SAE narrative:

- SAE description with all symptoms and laboratory/instrumental abnormalities and time frames indicated.
- Time after the last dose of the investigational product
- Autopsy data if the subject died (specify the cause of death according to postmortem report). If no autopsy findings are available, the cause of death should be specified according to the clinical conclusion.
- Time of hospitalization (if applicable)

8) Severity (CTCAE 4.03)

9) Seriousness

10) Medical history (with dates)

11) Investigations of particular interest at the onset of the SAE

- Investigation
- Normal limits
- Date of the analysis
- Result

12) Actions taken to resolve the SAE

- Medications/other

Translated from Russian to English, dated 26-Nov-2019

For medication therapy, the following should be specified: INNs and brand names of drugs, treatment start and stop dates, dosages, frequencies and routes of administration.

13) Actions taken regarding the investigational product

- Discontinued/dose reduced/unchanged etc.
- Dechallenge/rechallenge test results (if applicable)

14) Outcome

15) Signatures

The investigator **must** sign (with a signature and full name) each page of the SAE Report Form to verify his/her responsibility for the reported information. Signed SAE Report Form is then submitted to the Sponsor.

### **8.3.3. Reporting cases of study subject's pregnancy/study subject's partner's pregnancy**

In this study, the Investigator must report to the Sponsor all cases of study subject's pregnancy/study subject's partner's pregnancy that occurred during the study treatment period and follow-up after the last injection of BCD-085/placebo.

The forms are filled out in the following cases:

- When the initial information about the study subject's pregnancy/study subject's partner's pregnancy is obtained;
- When new important information (follow-up report) about the pregnancy (its complications or outcome) is obtained;
- In 6 months after the delivery, so that the baby's condition can be assessed.

The report about pregnancy NOT associated with an SAE should be sent to the Sponsor by e-mail to [REDACTED] within 5 working days.

If an SAE has developed during pregnancy, the Pregnancy Form with the information about the SAE must be sent to the Sponsor within 24 h after this information became available.

### **8.3.4. Recording administration errors with the investigational product**

Administration errors with the investigational product refer to any violation of dosing, route or procedure of administration described in the Study Protocol. This also includes violation (prolongation) of the interval between the doses of the investigational product, except for the cases specified by the protocol.

This form is filled out for all these errors except for overdoses.

If an administration error with the investigational product is associated with an SAE, an SAE Report Form should be also filled out.

If an investigational product administration error is not associated with an SAE, the Investigator should send the form by email to [[contact]](mailto:[contact]) within 5 working days.

If an administration error with the investigational product is associated with an SAE, two forms are filled out (SAE Report Form and IP Administration Error Report Form). Both forms must be sent to the Sponsor within 24 hours from the moment when this information became available.

### **8.3.5. Reporting drug overdose**

In this study, an overdose is defined the following way: administration of BCD-085 at a single dose greater than 120 mg or shortening of the interval between two doses by more than 3 days. Shortening the between-visit periods by 3 days or less is not considered an overdose.

Criteria for expedited reporting in case of overdoses:

- An overdose of 2-fold or more vs. the dose prescribed by the Investigator must be reported as part of expedited reporting whether it is associated with an AE/SAE or not;
- An overdose of less than 2-fold associated with an AE/SAE with a reasonable temporal relationship to the overdose also requires expedited reporting;
- An overdose of less than 2-fold not associated with AEs/SAEs may be reported to the Sponsor as part of expedited reporting if, in the opinion of the Investigator, this event is meaningful;

If the Investigator did not report an overdose of less than 2-fold using expedited reporting, the overdose should be recorded by the CRA only in the Deviations Log.

### **8.4. Methods and duration of follow-up for study subjects after the onset of AE/SAE**

If the patient is withdrawn from the study due to an AE/SAE, the investigator should perform further patient's treatment and follow-up as per standard institutional practices for the treatment of the certain AE or SAE. The patient should be followed up until **the AE/SAE resolves completely**. In case of any laboratory, instrumental or vital sign abnormality, the patient should, if possible, be followed up until the event is completely resolved (or until the value is back to the baseline level).

See section 5.4 for further details.

**The patient withdrawn from the study due to pregnancy** that occurred during the study should be monitored throughout the entire pregnancy and for 6 months after delivery to evaluate the mother's and child's health. Information on pregnancy course and outcome should be recorded in the source documentation. During the entire period of pregnancy, the investigator in collaboration with the attending Ob/Gyn Specialist should monitor the woman's overall health, the course of pregnancy, and laboratory values including ultrasound. When the child is born, the investigator together with the attending pediatrician should monitor the newborn for 6 months evaluating the child's clinical status and the laboratory/instrumental findings. The pregnancy course, its outcome, and the newborn are followed up only if the patient gives her consent in the written form. The consent should be signed by the patient and stored in the source documentation. Any time, the patient could refuse from the follow-up/providing information about her pregnancy/its outcome/the newborn.

**If the study subject's partner becomes pregnant**, the study subject should provide the contacts of attending Ob/Gyn Specialist to the Investigator. The investigator should monitor the woman's health over the entire course of pregnancy. Monitoring should be performed via phone calls to attending Ob/Gyn Specialist once every 3 months to analyze the overall woman's health, pregnancy course, and laboratory and instrumental findings including ultrasonic investigation. When the child is born, the investigator together with the attending pediatrician should monitor the newborn for 6 months evaluating the child's clinical status and the laboratory/instrumental findings. The pregnancy course, its outcome, and the newborn are followed up only if the woman gives her consent in the written form. The consent should be signed by the woman and stored in the source documentation. Any time, the woman may refuse from the follow-up/providing information about her pregnancy/its outcome/the newborn.

## 8.5. Immunogenicity study

To assess the immunogenic potential of the study treatment, the proportions of BAb- and NAb-positive patients will be estimated.

The immunogenicity endpoints will be evaluated at Weeks 12, 24, 54, 86, 110, 134, 154 (in patients of Arms 1 and 2) or 12, 24, 54, 64, 98, 122, 146, 166 (in patients of Arm 3).

The immunogenicity analysis will include all patients who have received at least one dose of BCD-085 and had an evaluable (not missing/lost/spoiled) serum sample taken before the first

## 9. STATISTICS

### 9.1. Description of statistical methods

The statistical analysis will be performed using two-sided hypothesis tests. The statistical significance level is 0.05.

To compare normally distributed data, it is planned to use the following tests: two-sample Student t-test, Welch's test, and ANOVA.

Non-normally distributed data will be compared with the following tests: Mann-Whitney test, Wilcoxon test, Kruskal-Wallis test, and Friedman test.

The quantitative data:

#### **Efficacy:**

- Relative PASI change,
- Change in itch severity (VAS, 0 to 100 mm),
- Change in NAPSI score,
- Change in quality of life according to the DLQI score,
- Time to loss of PASI 75/90/100, sPGA 0-1/sPGA 0, DLQI 0-1 response during the treatment with BCD-085.

#### **Safety:**

- CBC results,
- Blood chemistry results.

#### **Demographics**

will be tested for the normality of distribution using the Shapiro-Wilk test.

For normally distributed quantitative data, the following characteristics will be used: mean value, standard deviation, coefficient of variation, minimum and maximum. Non-normally distributed quantitative data will be described using median and quartiles, min and max values.

The categorical data:

#### **Efficacy:**

Translated from Russian to English, dated 26-Nov-2019

- Proportion of patients with PASI 75/90/100.
- Proportion of patients with sPGA score 0 or 1.
- Proportion of patients (among patients with psoriatic arthritis) who achieved an ACR20/50/70.
- Proportion of patients who maintained ACR 20/50/70 response (among patients with psoriatic arthritis).
- Proportion of patients who maintained DLQI score 0-1.

**Safety:**

- Proportion of patients who developed AEs/SAEs.
- Proportion of patients who developed injection site reactions.
- Proportion of patients who developed Grade 3/4 AEs/SAEs.
- Proportion of patients who discontinued the study due to AEs and/or SAEs.
- Exposure adjusted incidence rate of AEs/SAEs during the extension study.

**Immunogenicity:**

- Proportion of patients with anti-drug antibodies (binding/neutralizing)

will be processed using the frequency tables, Fisher's test,  $\chi^2$  test, and Cochran-Mantel-Haenszel test. The categorical data will be described using percentages or proportions.

For multiple comparisons, the Benjamini-Yekutieli procedure will be used. Regression will be used to assess the effects of the factors other than the therapy type. Time to loss of response will be assessed using log-rank test, Kaplan-Meier curves, and Cox regression model. Time will be counted from the response during the treatment with BCD-085. Right censoring can be used to analyze time to events.

Statistical methods will be chosen based on the type and distribution of raw data. Applicability of certain statistical tests will be evaluated after all the data are collected because it is impossible to predict the distribution pattern, data homogeneity and other data characteristics in advance.

The data will be processed using programming language R for statistical processing and SAS 9.4 software environment.

Translated from Russian to English, dated 26-Nov-2019

## 9.2. Statistical analysis steps and timelines for reports

### 9.3. Planned number of subjects. Justification of sample size, including reasoning or calculations to justify statistical power, and clinical justification of the study

Two independent hypotheses will be tested during the study:

1. The main study hypothesis (stating the non-inferiority of BCD-085 Q4W vs. BCD-085 Q2W) will be tested at the significance level of 0.05;
2. The hypothesis stating the superiority of BCD-085 in different dosing regimens over placebo will be tested at the significance level of 0.05.

### 9.3.1. Non-inferiority hypothesis

The sample size required to run the study was calculated on the basis of the literature data on clinical efficacy. During study planning, the hypothesis stating that BCD-085 Q4W is non-inferior to BCD-085 Q2W ( $H_0: \varepsilon \leq \delta$ ,  $H_1: \varepsilon > \delta$ , where  $\varepsilon$  is true difference in the frequency of the efficacy variable between the arms,  $\delta$  is non-inferiority margin) was tested with the following error values: type I error of 5% ( $\alpha=0.05$ ), type II error of 20% ( $\beta=0.2$ ), power of test of 80%. The

Translated from Russian to English, dated 26-Nov-2019

efficacy endpoint used to calculate the sample size was PASI 75 rate by Week 12 in each arm [REDACTED]

1. Efficacy variable in the arms: BCD-085 every 2 weeks ( $p_{2w}$ ) and BCD-085 every 4 weeks

( $p_{4w}$ ):

$p_{2w} = 0.891$  (89.1%)

$p_{4w} = 0.826$  (82.6%)

2. The true difference in the rates of the efficacy parameter between two regimens of BCD-085:

$$\varepsilon = p_{4w} - p_{2w} = 0.826 - 0.891 = (-0.065) (6.5\%)$$

3.  $z_{1-\alpha}$  and  $z_{1-\beta}$  – quantiles of normal distribution  $N(0,1)$  (mean: 0, standard deviation: 1).

4.  $k$  – coefficient for ratio between sample sizes [BCD-085 Q2W ( $n_{2w}$ ) to BCD-085 Q4W ( $n_{4w}$ )]:

$$n_{2w}/n_{4w} = k.$$

5. The non-inferiority margin for BCD-085 once every 4 weeks vs. BCD-085 once 2 weeks was considered to be the following:

$$\delta = (-0.2038) (-20.38\%)$$

[REDACTED]

[REDACTED]

[REDACTED]

[REDACTED]

[REDACTED]

[REDACTED]

[REDACTED]

[REDACTED]

[REDACTED]

After that, in accordance with the method described in [Chow Sh.-Ch., Shao J., Wang H., 2008], sample size was calculated using the assumption that sample sizes of the BCD Q4W ( $n_{4w}$ ) arm and the BCD Q2W ( $n_{2w}$ ) arm are the same, i.e.  $k = 1$ .

### 9.3.2. Superiority hypothesis

#### Sample size for superiority testing

During study planning, the hypotheses stating that BCD-085 Q4W and BCD-085 Q2W are superior to placebo ( $H_{01}:\varepsilon_{2w} \leq \delta$ ,  $H_{11}:\varepsilon_{2w} > \delta$ ;  $H_{02}:\varepsilon_{4w} \leq \delta$ ,  $H_{12}:\varepsilon_{4w} > \delta$ , where  $\varepsilon_{2w}$ ,  $\varepsilon_{4w}$  is the true difference in the rate of the efficacy variable between the arms treated with BCD-085 Q2W and with BCD-085 Q4W, respectively,  $\delta$  is the superiority margin for BCD-085 over placebo) were tested with the following error values: type I error of 5% ( $\alpha=0.05$ ), type II error of 20% ( $\beta=0.2$ ), power of test of 80%. The efficacy endpoint used to calculate the sample size was PASI 75 rate by Week 12 in each arm [REDACTED]

The sample size needed to test the superiority hypotheses was calculated using the method described by [Chow Sh.-Ch., Shao J., Wang H., 2008]:

1. Efficacy variable in the arms: BCD-085 every 2 weeks ( $p_{2w}$ ), BCD-085 every 4 weeks ( $p_{4w}$ ) and placebo ( $p_{pl}$ ):

$$p_{2w} = 0.891 \text{ (89.1\%)}$$

$$p_{4w} = 0.826 \text{ (82.6\%)}$$

$$p_{pl} = 0.039 \text{ (3.9\%)}$$

2. The true difference in the frequency of the efficacy variable between the test/comparator and placebo arms:

$$\varepsilon_{2w} = p_{2w} - p_{pl} = 0.891 - 0.039 = 0.852$$

$$\varepsilon_{4w} = p_{4w} - p_{pl} = 0.826 - 0.039 = 0.787$$

[figure not shown]
3.  $z_{(1-\alpha)}$  and  $z_{(1-\beta)}$  – quantiles of normal distribution  $N(0,1)$  (mean: 0, standard deviation: 1).
4.  $k$  – ratio between the test and control samples:

$$n_{p1}/n_{2w} = 1$$

$$n_{p1}/n_{4w} = 1$$

5. The superiority margin for BCD-085 (different regimens) over placebo was set as 0, as required to check the non-inferiority hypothesis in a placebo-controlled study:

$$\delta = 0.$$

Thus, the study should include at least 193 patients (77 in each BCD-085 arm and 39 in placebo arm). With a potential dropout rate of 10%, the study should involve 213 patients (85 patients in each BCD-085 arm and 43 patients in the placebo arm).

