#### 4.3.4. Randomization procedure

Randomization in the study will be centralized. Patients will be randomly assigned to three arms at a 2:2:1 ratio.

Patients included in the study will be randomized within each stratum (block randomization). Thus, after stratification, the arms will be balanced by all specified characteristics.

Block randomization can be described as follows. The random sequence generator generates infinite random sequences consisting of the numbers from 1 to 18 (1,2,3,4,5,6,7,8,9,10,11,12,13,14,15,16,17,18). Each number (1 to 18) corresponds to one of 18 possible unique blocks (see the table below). As the study design does not define in advance the exact number of patients in each of the 32 strata, the patients will be randomized within each stratum to assure the equal distribution between the arms. Therefore, each stratum will contain its own block sequence (symbols “1”, “2”, and “3” corresponding to the 2:2:1 distribution).

Translated from Russian to English, dated 26-Nov-2019

**Table 22.** Examples of blocks for block randomization.

Block	Principle of assigning to treatment arms
#1	1,1,2,2,3
#2	1,2,1,2,3
#3	1,2,2,1,3
#4	1,2,2,3,1
#5	1,2,3,2,1
#6	1,3,2,2,1
#7	3,1,2,2,1
#8	2,2,1,1,3
#9	2,1,2,1,3
#10	2,1,1,2,3
#11	2,1,1,3,2
#12	2,1,3,1,2
#13	2,3,1,1,2
#14	3,1,1,2,2

Block	Principle of assigning to treatment arms
# 15	3,1,2,1,2
#16	3,2,1,1,2
#17	3,2,1,2,1
# 18	3,2,2,1,1

These blocks consist of the following symbols: “1”, “2” and “3”, and each of them corresponds to the study arms, for example, “1” to Arm 1, “2” to Arm 2, “3” to Arm 3.

Finally, a table is generated containing a random block sequence. Each stratum is assigned an infinite random sequence of blocks (an example is shown in 23).

**Table 23.** An example of assigning strata with block sequence.

Stratum	Sequence of blocks
Stratum 1	#1
	6
	5
	2
	...
Stratum 2	4
	3
	5
	#1
	...
Stratum 3	5

Stratum	Sequence of blocks
	5
	#1
	4
	...
...	...

During randomization, the BIOCAD's Clinical Study Manager allocates the patient to an appropriate stratum, assigns him/her the first free arm number in the block and a 3-digit randomization number coding this arm (corresponds to the patient's order number in the study). After randomization, the Clinical Study Manager assigns the patient an investigational product lot number (corresponding to the treatment arm) and a Patient ID. The investigator will know only the subject's ID and investigational product lot number.

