#### **9.4. Suitable significance level**

The level of significance was set as 0.05 (5%) with the statistical power of 0.8 (80%).

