8.2. Description of the Statistical Methods to be Employed

The statistical analysis will be performed using two-sided hypothesis tests. The statistical significance level is 0.05.

The study hypothesis of non-inferior efficacy of BCD-085 once every 4 weeks vs. BCD-085 once every 2 weeks will be proved by comparing the lower bound of the 95% confidence interval for the difference in proportions of patients with PASI 75 at Week 12 between the BCD-085 Q4W and BCD-085 Q2W with pre-specified non-inferiority margin (δ) equal to -20.38%.

The hypothesis stating the superior efficacy of BCD-085 over placebo will be proved by comparing the lower bound of the 95% confidence interval for the difference in proportions of patients with PASI 75 by Week 12, in each BCD-085 arm and placebo arm, with pre-specified non-inferiority margin (δ , 0%).

Quantitative Data

The following quantitative data will be analyzed in the study:

Efficacy:

- Relative PASI change,
- Change in itch severity (VAS, 0 to 100 mm),
- Change in NAPSI score,
- Change in quality of life according to the DLQI score,

- Time to loss of PASI 75/90/100, sPGA 0-1/sPGA 0, DLQI 0-1 response during the treatment with BCD-085,

Safety:

- CBC results,
- Blood chemistry results,
- Vital signs,

Demographics and other baseline characteristics:

- General information (age, body weight, height, BMI),
- Duration of the disease, severity and the area of psoriasis (PASI), BSA, severity by sPGA, severity of nail psoriasis (NAPSI), severity of pruritus (VAS), quality of life score (DLQI), the presence of depression (Beck's score), functional activity (HAQ-DI), tender joint count (of 68), swollen joint count (of 66).

Quantitative data will be described using the following descriptive statistics: mean, SD, median, quartiles, CV, min, and max.

Quantitative variables will be tested for normality using the Shapiro-Wilk test.

Normally distributed quantitative variables will be tested using the two-sample Student's t-test, Welch's t-test, and ANOVA.

Non-normally distributed quantitative variables will be tested using the Mann-Whitney U-test, the Wilcoxon test, the Kruskal-Wallis test, and the Friedman test.

Time to loss of response will be assessed using log-rank test, Kaplan-Meier curves, and Cox regression model. Time will be counted from the response during the treatment with BCD-085. Right censoring can be used to analyze time to events.

Categorical Data

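### The 10% dropout allowance falls slightly short: 213 patients less 10% leave 191.7, below the plan's own minimum of 193, and the printed superiority ratio of 1 does not match the 2:2:1 randomization

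*Protocol*

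**What the plan says.** Protocol 9.3.2 closes the sample-size section with a minimum of 193 patients: 77 in each BCD-085 arm and 39 on placebo. It continues: "With a potential dropout rate of 10%, the study should involve 213 patients", made up of 85, 85 and 43. The Protocol synopsis and SAP 6.2 carry the same statement.

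Item 4 of Protocol 9.3.2 defines k as the "ratio between the test and control samples" and sets placebo over active equal to 1 for both regimens. Protocol 4.3.4 says: "Patients will be randomly assigned to three arms at a 2:2:1 ratio". The synopsis and SAP 3.1 give the same 2:2:1 allocation.

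Protocol 9.3.2 plans superiority at alpha 0.05 and 80% power, with assumed PASI 75 rates of 0.891 (Q2W), 0.826 (Q4W) and 0.039 (placebo). On the margin it says: "The superiority margin for BCD-085 (different regimens) over placebo was set as 0".

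**The concern.** A dropout allowance should ensure that, after the assumed loss, the required number remains. Adding 10% to the requirement does not do this, because the 10% is then lost from the larger, randomized number. Here the randomized totals fall below the minimum stated in the preceding sentence, so the two sentences cannot both be true.

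The ratio in item 4 is a second inconsistency in the same paragraph. A calculation with equal placebo and active arms cannot describe a trial with 39 against 77, and a reader cannot tell from it where the 39 comes from.

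What is at stake is the accuracy of the figures that justify the trial's size. The trial's ability to answer its questions is hardly affected.

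**Working it through.** **Inputs.** Minimum 193 = 77 + 77 + 39, dropout 10%, randomized 213 = 85 + 85 + 43 (Protocol 9.3.2, synopsis, SAP 6.2). Rates 0.891, 0.826 and 0.039, margin 0, alpha 0.05 with quantile z(1−alpha), power 80%, ratio 1 (Protocol 9.3.2). Allocation 2:2:1 (Protocol 4.3.4).

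**1. How the plan's figures arise.** Multiply the minimum by 1.10 and round up:
- total: 193 × 1.10 = 212.3, giving 213
- active arm: 77 × 1.10 = 84.7, giving 85
- placebo arm: 39 × 1.10 = 42.9, giving 43

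All three stated figures are reproduced exactly.

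**2. What remains after 10% dropout.**
- total: 213 × 0.90 = 191.7, against 193
- active arm: 85 × 0.90 = 76.5, against 77
- placebo arm: 43 × 0.90 = 38.7, against 39

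The shortfall is 1.3 patients in total, 0.5 in each active arm and 0.3 on placebo.

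**3. What 213 does tolerate.** 1 − 193/213 = 20/213 = 9.39%. By arm: 1 − 77/85 = 9.41% and 1 − 39/43 = 9.30%.

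**4. What 10% would have needed.** N/(1 − d):
- total: 193/0.90 = 214.4, giving 215
- by whole arms: 77/0.90 = 85.6, giving 86; 39/0.90 = 43.3, giving 44; 86 + 86 + 44 = 216

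That is 2 or 3 patients above 213.

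**5. The superiority ratio.** With margin 0 and equal arms, n per arm = (z(0.95) + z(0.80))² × [p(1 − p) + 0.039 × 0.961] / (p − 0.039)².
- Q2W: p = 0.891, difference 0.852, n = 1.15
- Q4W: p = 0.826, difference 0.787, n = 1.81

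Each rounds up to 2 per arm, so the printed superiority inputs cannot give 39. Allocation does: 77/2 = 38.5, which rounds up to 39.

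**6. Superiority power at the real sizes, 77 against 39.** Standardized effect = difference / √[p(1 − p)/77 + 0.039 × 0.961/39].
- Q2W: 0.852/√(0.001261 + 0.000961) = 0.852/0.0471 = 18.1
- Q4W: 0.787/√(0.001867 + 0.000961) = 0.787/0.0532 = 14.8

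Both lie far beyond the 1.645 used in planning and the 1.96 implied by a 95% confidence interval. Power exceeds 99.99% in each case.

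**The case against.** The strongest reply is that this is immaterial. The shortfall is 1.3 patients, efficacy is assessed in all randomized patients (Protocol 9.8, SAP 7), and no conclusion of the trial would change. This stands as to size. It does not rescue the sentence: the plan chose to state a minimum and a dropout rate, and its total does not satisfy both. Protocol 9.6 and SAP 8.4 also say that missing data will not be substituted, so the number of evaluable patients is a fair thing to state correctly.

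A second reply is that the closing sentence of 9.3.2 sums up all of 9.3, so 39 need not come from the superiority step, and that part of the working is blacked out. This stands too. Deriving the placebo arm from the allocation is legitimate. What remains is that the printed ratio is 1 and the trial's ratio is 0.5.

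Three stronger readings are tempting, and the documents do not support them.
- **That 77 was rounded down.** Exact quantiles with the printed non-inferiority inputs (rates 0.891 and 0.826, margin −0.2038) give 77.29 per arm. That value is printed nowhere and the working is redacted. With two-decimal quantiles the result is (1.64 + 0.84)² × (0.891 × 0.109 + 0.826 × 0.174)/(0.2038 − 0.065)² = 6.1504 × 0.240843/0.019265 = 76.89, which rounds up to 77. Rounding in the printed rates and margin alone moves the exact-quantile result between 76.2 and 78.4.
- **That superiority falls short of 80% power.** The 80% is a planning minimum, and the design exceeds it by a wide margin.
- **That the plan should now quote about 79.9% power for non-inferiority at 77 per arm.** That figure holds only at one-sided 5%. SAP 8.2 decides on the lower bound of a 95% confidence interval, where the same inputs give about 70% at 77 per arm. That mismatch is a separate matter, and a power figure that ignores it should not be added here.

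**Conclusion.** The dropout statement is wrong as written in all three places. The error is certain, because it needs only the plan's own four totals and the stated 10%, and multiplication by 1.10 reproduces every randomized figure. Its size is 1 to 2 evaluable patients, or a tolerance of about 9.4% where 10% is claimed. The ratio of 1 in Protocol 9.3.2 contradicts the 2:2:1 randomization but changes no number that matters. The power figures in step 6 assume the planned PASI 75 rates. Both points are minor corrections to the record, and neither is a reason to enlarge the trial.

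**What to change.** Make one wording edit in the Protocol synopsis, Protocol 9.3.2 and SAP 6.2:
- State that 213 patients (85, 85 and 43) allow for about 9.4% dropout from the minimum of 193. If the 10% is to be kept as a reference, add that it would have needed 215 in total, or 216 by whole arms (86 + 86 + 44).
- In Protocol 9.3.2, item 4, change the placebo-to-active ratio from 1 to 0.5 for both regimens. Make the same change in SAP 6.2 if its blacked-out working repeats the ratio.
- Add a sentence saying that the placebo size of 39 follows from the 2:2:1 allocation (half of 77, rounded up), and that superiority power at 77 against 39 is far above the 80% planning minimum.

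The cost is wording only. No patients are added and no analysis changes. The stated dropout tolerance becomes slightly less favourable.
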